6.2 Subject Disposition and Data Sets Analyzed

Patient disposition will be listed and summarized by treatment group and overall and will include the number and percentage of patients:

- Entered Safety Period
- Completed Study
- **Entered Taper Period**
- Entered Follow-up Period

In addition, the number and percentage of patients who complete the study and who discontinue early, including a breakdown of the primary reasons for discontinuation from the study will be presented.

A summary of patient enrollment by site will also be provided by treatment group and overall for the enrolled population.

A listing of study drug bottle numbers and assignments will be produced.

Sponsor Name: Insys Development Company, Inc.

Sponsor Protocol ID: INS011-17-115 Covance Study ID: 000000163385

6.3 Protocol Deviations

All important protocol deviations will be listed and summarized by treatment group for the enrolled population.

6.4 Demographics and Other Baseline Characteristics

Demographic and baseline characteristics will be listed and summarized by treatment group and overall for enrolled population. Standard descriptive statistics will be presented for the continuous variables of:

- age (years);
- gender (Male, Female);
- ethnicity (Hispanic or Latino, Not Hispanic or Latino, Unknown);
- race (White, Black or African American, Asian, American Indian or Alaska Native, Native Hawaiian or other Pacific Islander, Other);
- weight (kg) at Day 1 visit;
- height (cm) at Day 1 Visit;
- body mass index (kg/m²) (derived on eCRF);

No formal tests of statistical significance will be performed on the demographic and baseline data.

Other baseline measurements, such as vital signs and ECG, will be summarized by treatment group with the post-baseline measurements.

6.4.1 Medical or Surgical History

Medical or surgical history will be coded using the Medical Dictionary for Regulatory Activities (MedDRA) [Version 21.1 (or a later version if updated during the study)]. All medical history or surgical history will be listed, and the number and percentage of patients with any medical or surgical history will be summarized for all enrolled population by system organ class (SOC) and preferred term (PT) for each treatment group and overall.

6.4.2 Prior and Concomitant Medications

Medications received prior to or concomitantly with treatment will be coded by Covance using the WHO Drug Dictionary [Version March 2018 (or a later version if updated during the study)], Anatomical Therapeutic Chemical (ATC) Classification codes.

Prior medications and concomitant medications are defined as follows:

Prior medications are those prior to the first dose date of IMP treatment on INS011-16-085.

Sponsor Name: Insys Development Company, Inc.

Sponsor Protocol ID: INS011-17-115 Covance Study ID: 000000163385

Concomitant medications are those with a start date on or after the first dose date of IMP treatment on INS011-16-085, or those with a start date before the first dose date of IMP treatment and a stop date on or after the first dose date of IMP treatment or ongoing end of study.

If a medication cannot be classified as "prior" or "concomitant" after applying imputation rules for missing/incomplete dates, it will be classified as concomitant.

Prior medications and concomitant medications will be listed together and summarized separately for enrolled population.

The number and percentage of patients using each medication will be displayed together with the number and percentage of patients using at least one medication within each therapeutic class (ATC-Level 2), chemical subgroup (ATC-Level 4), and generic term.

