5.1 Time points and Visit Windows

Day 1 is defined as the date of enrollment onto INS011-17-115 study. Relative days after Day 1 are calculated as (assessment date – Day 1 date) + 1. Relative days prior to Day 1 are calculated as (assessment date – Day 1 date). The day prior to Day 1 is Day -1.

All data will be analyzed using nominal study visits as defined in the Study Schedule (see Appendix A). No visit windows will be applied for summary and analysis.

Multiple visits within the same protocol-defined scheduled window (see Appendix A) will be dealt with as follows:

• If multiple scheduled visits occur within a single protocol-defined visit window then the visit closest to the target day of the visit window will be used in the analysis. In cases where the measurements are equal distances from the target day, the later visit will be used in the analysis.

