6.7.2 Adverse Events

All AEs recorded on the eCRF will be coded using the MedDRA dictionary [Version 21.1 (or a later version if updated during the study)] and classified as treatment – emergent AEs (TEAEs) as follows:

• TEAEs are events with start date on or after the date of first dose of IMP and up to 14 days after the last dose of IMP or events with start date prior to the date of first dose of IMP whose severity worsens on or after the date of first dose of IMP on INSO11-17-115.

All AE data will be listed by treatment group. Treatment-emergence status will be flagged in the listing. In addition, corresponding listings of treatment-emergent serious AEs (TESAEs), AEs leading to permanent discontinuation of IMP and AEs resulting in death will be produced. AE ongoing or worsened from INS011-16-085 will be listed.

Summary tables of TEAEs by treatment group and overall will be produced for the enrolled population. No statistical comparisons of AEs between treatment groups will be performed.

The severity of all AEs is recorded as mild, moderate, or severe. If severity is missing for a TEAE, it will be considered severe.

The relationship between an AE and IMP treatment is assessed as definite, probable, possible, unlikely or not related. A treatment-related AE is an AE considered by the investigator as definitely, possibly, or probably related to IMP treatment or with unknown/missing relationship to IMP treatment.

An overview table will summarize the number and percentage of patients with at least one of the following TEAEs, where patients with more than one TEAE in a particular category are counted only once in that category:

Sponsor Name: Insys Development Company, Inc.

Sponsor Protocol ID: INS011-17-115 Covance Study ID: 000000163385

- any TEAE;
- TEAE by severity (mild, moderate, severe);
- treatment-related TEAE;
- severe treatment-related TEAE;
- TESAE;
- TESAE by severity;
- treatment-related TESAE;
- TEAE leading to study drug discontinuation.

The overview table will be repeated to summarize the number of TEAEs (displaying the number and percentage of observed events).

The number and percentage of patients reporting each AE will be summarized by System Organ Class (SOC) and Preferred Term (PT) for all enrolled patients. Tables will be sorted alphabetically by SOC. PTs will be sorted by descending overall total. The following summaries will be produced:

- TEAEs, by SOC and PT;
- TEAEs related to IMP treatment, by SOC and PT;

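### SAP 6.4.2 dates prior and concomitant medication from the first dose in the parent trial, so a medicine stopped before this trial's first dose is summarised as concomitant, on a different clock from the TEAEs

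*SAP*

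**What the plan says.** SAP 6.4.2 gives two definitions, both tied to the parent trial:

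- Prior: "Prior medications are those prior to the first dose date of IMP treatment on INS011-16-085".
- Concomitant, first limb: "Concomitant medications are those with a start date on or after the first dose date of IMP treatment on INS011-16-085".
- Concomitant, second limb: an earlier start with "a stop date on or after the first dose date of IMP treatment or ongoing end of study". This limb does not name the trial. In context it is the parent trial.

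Neither limb requires any use on or after Day 1 of this trial, and neither has an upper time limit.

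Other parts of the plan use this trial's clock. SAP 5.1: "Day 1 is defined as the date of enrollment onto INS011-17-115 study". SAP 6.7.2: "TEAEs are events with start date on or after the date of first dose of IMP and up to 14 days after the last dose", with worsening of earlier events counted only for those "whose severity worsens on or after the date of first dose of IMP on INSO11-17-115". Carry-over events are handled apart: "AE ongoing or worsened from INS011-16-085 will be listed".

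The partial-date rule for medications in SAP 5.2 uses a third anchor, the start of double-blind treatment, although this trial is open-label. Protocol 8.5.1.3 asks for prior and concomitant medications to be summarised but sets no cut-off date. SAP section 7 declares no change to the planned analysis.

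**The concern.** This is an uncontrolled safety trial. The co-medication summary is one of the few means of judging whether an event might be due to background treatment. It should describe what patients took while they were in this trial.

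Under SAP 6.4.2 it also describes what they took, and finished, in the parent trial. Three things follow if those records are present. Concomitant use is overstated for this trial. The prior table stops at the parent trial's first dose, so it omits the months just before Day 1, which are the history a reader most wants. And an illness and its treatment can be split: the event is outside the treatment-emergent window, while the medicine given for it is tabulated as concomitant. Because SAP 6.1 presents tables by modal dose, such a medicine would also be shown under a dose group that reflects later dosing.

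**Working it through.** The plan gives no figure to reproduce here. The check has two parts: classify medication histories under each anchor, then size the look-back.

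**Classification.** Let F be the first dose in INS011-16-085 and D the first dose in INS011-17-115, with F before D. Dates are complete. The rule in SAP 6.4.2 is: concomitant if start ≥ F, or if start < F and stop ≥ F (or ongoing); otherwise prior. The comparison rule replaces F by D.

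| Medication history | Anchor F (SAP 6.4.2) | Anchor D |
|---|---|---|
| Stopped before F | prior | prior |
| Started and stopped during the parent trial | concomitant | prior |
| Started before F, stopped during the parent trial | concomitant | prior |
| Started during the parent trial, ongoing | concomitant | concomitant |
| Started before F, ongoing | concomitant | concomitant |
| Started in this trial | concomitant | concomitant |

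Two of six histories change class, whatever the parent trial's length. The second row follows from the first limb alone, which names the parent trial. The third row depends on reading the unnamed first dose in the second limb as the parent trial's.

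**Against the adverse-event clock.** Take an event with the same dates as the second row. It starts and ends before D, so it is not treatment-emergent under SAP 6.7.2. The sentence there names INS011-17-115 only at its end, but the separate listing of events carried over from the parent trial supports that reading for the whole definition.

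**Size of the look-back.** Inputs:

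- Safety Period of 48 weeks and taper of 6 days (Protocol 3.1, nominal values): 48 × 7 + 6 = 342 days.
- Gap between the trials of 0 to 14 days (SAP 2.2 allows up to 2 weeks).
- Time L from first dose to Visit 10 in the parent trial: not given. Assumed at 4, 12 and 26 weeks to show a range.
- First dose in this trial taken as Day 1.

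Look-back = 7L + gap. Share of window before Day 1 = look-back / (look-back + 342).

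| L (weeks) | Gap (days) | Look-back (days) | Share before Day 1 |
|---|---|---|---|
| 4 | 0 | 28 | 28/370 = 7.6% |
| 4 | 14 | 42 | 42/384 = 10.9% |
| 12 | 0 | 84 | 84/426 = 19.7% |
| 12 | 14 | 98 | 98/440 = 22.3% |
| 26 | 0 | 182 | 182/524 = 34.7% |
| 26 | 14 | 196 | 196/538 = 36.4% |

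These are shares of time, not of patients or records.

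**The case against.** The strongest reply is that the anchor is deliberate. This is a rollover study meant to avoid a break in treatment, baseline is also set in the parent trial (Visit 10), and SAP 6.4.2 names the parent trial in both definitions. A look-back to first exposure is defensible in an extension. That stands as far as it goes, but the SAP gives no reason for it, does not label the tables that way, and does not apply it to adverse events.

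Second, nothing may change in practice. The documents do not say whether parent-trial medication records enter this database, and Visit 1 only calls for a review of concomitant medications (Protocol 7.1.1). This stands, and the point is limited accordingly.

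Third, a reader might infer that the tables will show prohibited use that never happened here, or that they cannot be set against the TEAE tables at all. The documents do not support either reading in full. Important deviations are listed and summarised separately (SAP 6.3). Prior and concomitant medications are listed together, and listings run by patient and date (SAP 6.1), so timing can be checked patient by patient. Growth hormone, thyroid and psychotropic treatment that is ongoing at Day 1 is concomitant under either anchor. What remains is that the summary percentages themselves would mix two periods.

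Fourth, the missing upper limit might suggest cutting concomitant use at last dose plus 14 days, to match the TEAE window. The protocol points the other way: section 4.7.2 restricts medication through the Follow-up Period, and the Visit 9 call still collects it (section 7.4).

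**Conclusion.** The point holds as a defect in a stated rule. With complete dates, SAP 6.4.2 puts a medicine used in the parent trial and stopped before the first dose here into the concomitant table and keeps it out of the prior table, while Day 1 and the TEAEs run on INS011-17-115. This follows from the text and does not depend on any assumed duration.

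The effect on reported percentages is unknown. It depends on the length of parent treatment, on how often short courses occur, and on whether parent-trial records are in this database; none of these is given. The range of about 8% to 36% of the window before Day 1 rests on the assumed 4 to 26 weeks. A reader might take the 12-week study length mentioned in Protocol 1.2.2.2, add a course rate, and quote a specific inflation. That text does not name INS011-16-085, and no rate appears in the documents, so such a figure would be illustration only.

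Only descriptive tables are affected. Sample size and inferential results are untouched. The change should be made before database lock because it is cheap and the rule misclassifies as written.

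**What to change.** 1. In SAP 6.4.2, anchor both definitions to the first IMP dose in INS011-17-115. Prior: stopped before that dose. Concomitant: taken at any time on or after that dose through the Follow-up Period.
2. Flag medicines first started after the last dose as post-treatment, and still summarise them, since restrictions and collection run through follow-up.
3. In SAP 5.2, replace the double-blind anchor for medications with the same date. SAP 6.4.2 relies on those rules, so changing it alone leaves a conflict. At the same time, reconcile the class for unresolved records: SAP 5.2 allows both prior and concomitant, whereas SAP 6.4.2 sends them to concomitant only.
4. If the sponsor wants the parent-trial look-back, show it as a separate, labelled column or flag, and state whether parent-trial medication records are brought into this database.

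Cost: edits to two SAP sections and a small derivation change, with no new data to collect. Reported concomitant use becomes slightly lower, and the prior table gains the medicines stopped during the parent trial, where those records are held.

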6.5 Measurements of Treatment Compliance

Percentage compliance is calculated based on the study drug administration page as follows:

$$100 imes rac{ ext{\# doses taken}}{ ext{Expected \# doses (based on visit days)}}$$

where # doses taken = # of the "yes" responses to "Was AM dose taken?" and "Was PM dose taken?"

Percentage compliance will be summarized descriptively by treatment group for the enrolled population.

The following percentage compliance categories will also be presented:

- <90.0%
- \geq 90.0% and \leq 110.0%
- >110.0%

In addition, summary statistics of the weights of bottles dispensed and returned, as well as the volume administered, will be presented by treatment group for the enrolled population.

All study drug administration and drug accountability data will be listed in full.

6.6 Efficacy

All statistical inference will be based on a comparison of the CBD treatment groups. Descriptive statistics for efficacy endpoints will be based on all treatment groups, i.e. CBD (20 mg/kg/day), CBD (30 mg/kg/day), CBD (40 mg/kg/day), and all CBD.

Sponsor Name: Insys Development Company, Inc.

Sponsor Protocol ID: INS011-17-115 Covance Study ID: 000000163385

6.6.1 Exploratory Efficacy Analysis

Total HQ-CT scores and changes from baseline will be summarized by treatment group and visit using standard descriptive statistics.

6.6.2 Sensitivity Analysis

Not applicable.

6.6.3 Secondary Efficacy Analysis

Not applicable.

6.6.4 Subgroup Analysis

Not applicable.

6.6.5 Columbia Suicide Severity Rating Scale

Responses Columbia Suicide Severity Rating Scale (C-SSRS) will be listed separately for the adult and child-completed assessments. The listings will be based on the enrolled population.

C-SSRS will be categorized based on the Columbia Classification Algorithm of Suicide Assessment (C-CASA) categories 1, 2, 3, 4 and 7 as follows (Gassmann-Mayer, et al., 2011):

Event code	C-CASA event	C-SSRS event ^a	
1	Suicide completed	Completed suicide	
2	Suicide attempt	Actual attempt	
3	Preparatory actions towards	Interrupted attempt	
	imminent suicidal behaviour (including interrupted attempt or aborted attempt)	Aborted attempt	
		Preparatory acts or behavior	
4	Suicidal ideation	Subscale code and event:	
		 Wish to be dead Non-specific active suicidal thoughts Active suicidal ideation with any methods (not plan) without intent to act Active suicidal ideation with some intent to act, without specific plan Active suicidal ideation with any specific plan and intent 	
7	Self-injurious behavior	Has the subject engaged in non-	

Sponsor Name: Insys Development Company, Inc.

Sponsor Protocol ID: INS011-17-115 Covance Study ID: 000000163385

without suicidal intent	suicidal self-injurious behavior?
-------------------------	-----------------------------------

^aAn event corresponds to a "yes" response to the C-SSRS question.

C-SSRS will be summarized as dichotomous endpoints corresponding to the C-CASA categories at Visit 1 and End of Study/Early Withdrawal Visits.

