1.4. Prader-Willi Syndrome

Prader-Willi Syndrome (PWS), first described in 1956, is a multifaceted developmental disorder and the most common genetic syndrome associated with obesity (Gunay-Aygun et al., 1997; McAllister and Whittington, 2011). It is caused by the absent expression of paternally-inherited genes in the PWS region on 15q11-q13 (Ledbetter et al., 1981). While it presents with generalized hypotonia and developmental delay in infancy, PWS then manifests with uncontrollable appetite, hyperphagia, and excessive weight gain leading to severe obesity (Grechi et al., 2012).

Clinically, PWS patients suffer a complex pattern of physical, behavioral, endocrine, and intellectual deficiencies. Endocrine abnormalities lead to hypogonadism and short stature. In particular, growth hormone deficiency is reported to occur in 40% to 100% of the population (Griggs et al., 2015) and is commonly treated with growth hormone (Angulo et al., 2015). Behavioral disorders include obsessive compulsive behaviors such as skin picking, hoarding, redoing, and repetitive speech (Griggs et al., 2015).

However, it is the appetite behavior classified as hyperphagia in Prader-Willi Syndrome that is the most life threatening (Dykens et al., 2007; Griggs et al., 2015) and until recently, no patient lived over the age of 50 due to morbid obesity and its related complications (Aycan et al., 2014). The mortality rate in patients with PWS is six times higher than patients with other intellectual disabilities (Einfeld and Kavanagh, 2006) and mortality in patients not treated with growth hormone was estimated to be 3% per year between the ages of 6 and 56 compared to the general population mortality of 0.13% below 55 years. Mortality in Prader-Willi Syndrome below 5 years of age has not been determined (Eiholzer, 2005).

Hyperphagic behaviors can also be dangerous in persons who are not obese, with increased risks of death due to choking while sneaking food, and gastric perforations after consuming more food than usual (Dykens et al., 2007). Approximately 8% of deaths in individuals with PWS are reported due to the choking, especially on hot dogs (Stevenson et al., 2007). PWS patients also are known to eat discarded (contaminated) food and items that are not for human consumption such as pet food, or even non-food items such as paint or paper (Griggs et al., 2015).

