3.1.1. Safety Assessments

At Visit 1 (Day 1) and each monthly and quarterly visit, the following assessments will be completed:

- Review vital signs, clinical labs, ECG, urinalysis (Visit 1 only), urine preganacy screen, urine drug screen, weight and physical examination.
- Review concomitant medication and adverse events (AEs).
- 12-lead ECG.

- Columbia-Suicide Severity Rating Scale (C-SSRS) will be used for children and adolesents aged 7 to 17 years, if appropriate.
- Dispensing CBD.
- Drug accountability.

At Visit 7 (End of Study) or Early Withdrawal Visits the following assessments will be completed:

- Review vital signs, clinical labs, ECG, urinalysis, urine preganacy screen, urine drug screen, weight and physical examination.
- Review concomitant medication and adverse events (AEs).
- 12-lead ECG.
- Columbia-Suicide Severity Rating Scale (C-SSRS) will be used for children and adolesents aged 7 to 17 years, if appropriate.
- Hyperphagia Questionnaire for Clinical Trial (HQ-CT).
- Dispensing CBD.
- Drug accountability.

All AEs that arise during the Safety, Taper, and Follow-up Periods will be documented.

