6.1.5. Columbia Suicide Severity Rating Scale (C-SSRS)

The C-SSRS is a prospective assessment tool routinely used in studies of drugs with any potential for CNS effects. It captures the occurrence, severity, and frequency of suicide-related thoughts and behaviors during the assessment period. The questionnaire will be completed during Visit 1 (Day 1) and at the end of the Safety Period (Visit 7) or Early Withdrawal Visit.

Patients who have significant findings for suicidal ideation as assessed by the C-SSRS must be referred to the investigator for follow-up evaluation.

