8.5.3.6. Columbia Suicide Severity Rating Scale (C-SSRS)

C-SSRS categorization based on Columbia Classification Algorithm of Suicide Assessment (C-CASA) categories 1, 2, 3, 4, and 7 will be summarized as dichotomous endpoints at Visit 1 (Day 1) and End of Study/Early Withdrawal Visits.

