6.1 General Principles

All data processing, summarization and analyses will be performed using Covance's SAS Environment / Version 9.4 (or later) of the SAS® statistical software package.

The analysis treatment group will be defined by the modal dose of study drug (dose of the study drug that the patient took for the longest period).

The following principles will be applied to all TFLs unless otherwise stated:

Principle	Value		
Significant tests	Two-sided and use a 5% significance level		
Treatment group labels	Listings:		
and order presented	Cannabidiol Oral Solution (20mg/kg/day)		
	Cannabidiol Oral Solution (30 mg/kg/day)		
	Cannabidiol Oral Solution (40 mg/kg/day)		
	Tables:		
	CBD (20 mg/kg/day)		
	CBD (30 mg/kg/day)		
	CBD (40 mg/kg/day)		
	All CBD		
Tables	Data in summary tables presented by treatment group and visit (where applicable)		
Listings	All data collected presented by		
	Treatment group		
	Patient		
	Visit (where applicable)		
	Date;		
	unless otherwise specified		
Descriptive summary	Number of patients/observations (n)		
statistics for continuous variables	Mean		
	Standard deviation (SD)		

Sponsor Name: Insys Development Company, Inc.

Sponsor Protocol ID: INS011-17-115 Covance Study ID: 000000163385

Principle	Value
	Median
	Minimum
	Maximum
Descriptive summary statistics for categorical variables	Frequency counts and percentages [n (%)]
Denominator for percentages	Number of patients in the analysis population, unless stated otherwise in table shell(s)
Include "Missing" as	Yes, when the number missing is greater than zero for at
category	least one treatment group
Display for 0	Leave blank
percentages	
Display to one more decimal place than collected value	Mean Mean Difference
	Median Percentages
Display to two more	Standard Deviation
decimal places than collected value	Confidence Interval
Limit of precision for displays	3 decimal places

Baseline is defined as Visit 10 of INS011-16-085.

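### The C-SSRS summary tables give separate Visit 1 and end-of-study percentages, which cannot separate new-onset from pre-existing cases; the protocol's age wording for the scale also conflicts with its own schedule

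*SAP*

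**What the plan says.** **Tables.** SAP 6.6.5 maps the scale to C-CASA categories 1, 2, 3, 4 and 7 and then says "C-SSRS will be summarized as dichotomous endpoints corresponding to the C-CASA categories at Visit 1 and End of Study/Early Withdrawal Visits". Protocol 8.5.3.6 agrees: the categories "will be summarized as dichotomous endpoints at Visit 1 (Day 1) and End of Study/Early Withdrawal Visits". Under SAP 6.1, categorical data are shown as counts with percentages, by modal-dose group and visit. Neither document specifies a shift, change or new-onset table for the scale.

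**Listings.** The same SAP section says that responses "will be listed separately for the adult and child-completed assessments". SAP 6.1 orders listings by treatment group, patient, visit and date.

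**Other safety data.** SAP 6.7.3 to 6.7.6 plan shifts from baseline for laboratory values, vital signs, the investigator's ECG assessment and physical examination.

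**Who is assessed.** Protocol 3.1.1, in its list for Visit 1 and the interim visits and again in its list for Visit 7/Early Withdrawal, says "Columbia-Suicide Severity Rating Scale (C-SSRS) will be used for children and adolesents aged 7 to 17 years, if appropriate". Protocol 6.1.5 has no age limit: "The questionnaire will be completed during Visit 1 (Day 1) and at the end of the Safety Period (Visit 7) or Early Withdrawal Visit". Protocol Table 1 and SAP Appendix A also schedule the scale without one.

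**The concern.** A long-term safety study should be able to say how many patients developed suicidal ideation or behaviour during follow-up. That is a within-patient question. The planned tables give the proportion positive at the start and the proportion positive at the end, without linking them. Equal percentages could be read as no change even if all the patients positive at the end were new and all those positive at the start had resolved. The SAP handles this correctly for four other kinds of safety data. The scale is placed under section 6.6 (Efficacy), outside section 6.7 where those shift tables are specified.

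The age wording matters for the same reason. Pairing needs both assessments. A site that followed Protocol 3.1.1 to the letter could skip the Visit 7 assessment of a patient who had turned 18, and an assessment not done cannot be recovered at analysis.

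**Working it through.** There is no planned figure to reproduce. The 66 in SAP 2.3 is a roll-over maximum, and the analysis of the scale is descriptive.

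**1. What two separate percentages say about new cases.** Let N = 66 (SAP 2.3), with all patients assumed assessed at both visits. Let a be the number positive at Visit 1 and b the number positive at the end. The number who are negative at Visit 1 and positive at the end lies between max(0, b − a) and min(b, N − a). The counts below are hypothetical, because the documents give none.

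| a | b | Fewest new | Most new | As % of those negative at Visit 1 |
|---|---|---|---|---|
| 3 (4.5%) | 3 (4.5%) | 0 | 3 | 0% to 4.8% of 63 |
| 4 (6.1%) | 4 (6.1%) | 0 | 4 | 0% to 6.5% of 62 |
| 6 (9.1%) | 6 (9.1%) | 0 | 6 | 0% to 10.0% of 60 |
| 6 (9.1%) | 3 (4.5%) | 0 | 3 | 0% to 5.0% of 60 |
| 3 (4.5%) | 6 (9.1%) | 3 | 6 | 4.8% to 9.5% of 63 |

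In each row the planned table looks the same across the whole range. A cross-tabulation of the two visits gives the exact count.

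**2. How many patients the age wording could touch.** Treatment lasts 48 weeks (Protocol 3.1): 48 × 7 / 365.25 = 0.92 years. If ages at Visit 1 are uniform over a span of S years ending just below 18, the expected number turning 18 by Week 48 is 66 × 0.92 / S.

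- Ages 8 to <18 (S = 10): 66 × 0.092 = 6.1, about 6 patients (9.2%).
- Ages 10 to <18 (S = 8): 66 × 0.115 = 7.6, about 8 patients (11.5%).
- Ages 12 to <18 (S = 6): 66 × 0.153 = 10.1, about 10 patients (15.3%).

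The range 8 to 17 comes from the pharmacokinetic background in Protocol 1.3.1. The eligibility criteria in Protocol 3.2 set no age limit. The uniform spreads are assumptions, and the calculation uses the maximum enrolment with no early withdrawals.

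**3. The age passages side by side.** Protocol 3.1.1 gives ages 7 to 17, qualified by a clause leaving room for judgement. Protocol 6.1.5, Table 1 and SAP Appendix A give no limit. SAP 6.6.5 provides for adult assessments. These cannot all be applied to a patient aged 18 at Visit 7.

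**The case against.** **The listings already answer the question.** A reader might infer that new onset cannot be determined at all. The documents do not support that. Responses are listed by patient and visit for at most 66 patients, so each new positive can be read off. What is missing is a summary table; no information is lost. Two limits remain: a listing gives neither a new-onset count nor a denominator, and SAP 6.6.5 does not say whether adult and child refer to the patient's age or to the respondent. If it is the patient's age, someone who turns 18 has the two assessments in different listings.

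**Adverse event reporting is a second route.** Significant ideation must be referred to the investigator (Protocol 6.1.5), and a new or worsening illness is an adverse event (Protocol 6.1.7.1). This helps, but neither document says that a positive answer on the scale is to be recorded as an adverse event. It is also fair that the scale is not among the safety endpoints in Protocol 8.1 or SAP 3.1.

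**The age limit is one qualified phrase.** A reader might infer that the plan takes the end-of-study assessment away from patients who turn 18. That is not established: Protocol 7 refers to Table 1 for the assessments to be done, and Table 1 has no limit. If 8 to 17 was the range at entry to the parent study, some patients could already be 18 at Visit 1, which the figures above do not cover.

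**Skin picking.** The protocol says "Behavioral disorders include obsessive compulsive behaviors such as skin picking, hoarding, redoing, and repetitive speech", and a reader might infer that long-standing skin picking will fill category 7 and hide new self-injury. Nothing in the documents says that skin picking is scored on that item, or that a description is collected that would identify it. Category 7 already has its own endpoint.

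**Conclusion.** The point holds for the summary tables. As planned, they cannot separate new-onset from pre-existing cases: 4 positives at each visit leaves 0 to 4 new ones, and only the patient listings can settle which. This is a modest gap in presentation, out of line with how the SAP treats other safety data and cheap to close.

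The age wording is a real inconsistency. Read literally, Protocol 3.1.1 would omit the assessment for patients aged 18 or over at a visit. About 6 of 66 would turn 18 by Week 48 if ages are uniform over 8 to <18, and about 10 if uniform over 12 to <18; both spreads are assumed.

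One limit applies to any remedy. Patients roll over so that treatment is not interrupted (SAP 2.2), so Visit 1 is not necessarily a drug-free baseline. A positive at Visit 1 may have arisen on drug in the parent study. New onset here means new since Visit 1.

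**What to change.** In SAP 6.6.5, add a table of Visit 1 status by End of Study/Early Withdrawal status for each C-CASA category and for any of categories 1 to 4, by modal-dose group and overall. Include a new-onset count whose denominator is the patients negative at Visit 1 who have a later assessment, and show the number who cannot be paired. State that the reference is Visit 1 of this study, since SAP 6.1 defines baseline elsewhere as Visit 10 of the parent study, and that Visit 1 follows the parent study and is not necessarily drug-free. Say what adult and child mean in the listings.

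Reconcile the age wording of Protocol 3.1.1 with Protocol 6.1.5, Table 1, SAP Appendix A and the adult listing in SAP 6.6.5, so that every patient assessed at Visit 1 can be paired.

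The cost is a few lines of SAP text, one table from data already scheduled for collection and one reconciled protocol statement. No visit is added to the schedule in Table 1.
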